### Local Skin Tolerability Assessment

Reaction	NONE	Mild	Moderate	Severe	Measurement (if applicable)
Erythema*					
Edema*					
Induration*					
Itching					
Pain or Tenderness*					
Other: _____					

\* If present, region will be measured, length and width as appropriate.

Initials: \_\_\_\_\_

## APPENDIX 5. ADVERSE EVENTS: DEFINITIONS AND PROCEDURES FOR RECORDING, EVALUATING, FOLLOW-UP, AND REPORTING

### Definition of Adverse Event (AE)

AE Definition

• An AE is any untoward medical occurrence in a patient or clinical trial patient, temporally associated with the use of trial treatment, whether or not considered related to the trial treatment.

• NOTE: An AE can therefore be any unfavorable and unintended sign (including an abnormal laboratory finding), symptom, or disease (new or exacerbated) temporally associated with the use of trial treatment.

Events Meeting the AE Definition

• Any abnormal laboratory test results (hematology, clinical chemistry, or urinalysis) or other safety assessments (eg, ECG, radiological scans, vital signs measurements), including those that worsen from baseline, considered clinically significant in the medical and scientific judgment of the investigator (ie, not related to progression of underlying disease).

• Exacerbation of a chronic or intermittent pre-existing condition including either an increase in frequency and/or intensity of the condition.

• New conditions detected or diagnosed after trial treatment administration even though it may have been present before the start of the trial.

• Signs, symptoms, or the clinical sequelae of a suspected drug-drug interaction.

• Signs, symptoms, or the clinical sequelae of a suspected overdose of either trial treatment or a concomitant medication. Overdose per se will not be reported as an AE/SAE unless it is an intentional overdose taken with possible suicidal/self-harming intent. Such overdoses should be reported regardless of sequelae.

• “Lack of efficacy” or “failure of expected pharmacological action” per se will not be reported as an AE or SAE. Such instances will be captured in the efficacy assessments. However, the signs, symptoms, and/or clinical sequelae resulting from lack of efficacy will be reported as AE or SAE if they fulfil the definition of an AE or SAE.

Events NOT Meeting the AE Definition


• Any clinically significant abnormal laboratory findings or other abnormal safety assessments which are associated with the underlying disease, unless judged by the investigator to be more severe than expected for the patient’s condition.

• The disease/disorder being studied or expected progression, signs, or symptoms of the disease/disorder being studied, unless more severe than expected for the patient’s condition.

• Medical or surgical procedure (eg, endoscopy, appendectomy): the condition that leads to the procedure is the AE.

• Situations in which an untoward medical occurrence did not occur (social and/or convenience admission to a hospital).

• Anticipated day-to-day fluctuations of pre-existing disease(s) or condition(s) present or detected at the start of the trial that do not worsen.

### Definition of Serious Adverse Event (SAE)

If an event is not an AE per definition above, then it cannot be an SAE even if serious conditions are met (eg, hospitalization for signs/symptoms of the disease under trial, death due to progression of disease).

An SAE is defined as any untoward medical occurrence that, at any dose:	
a. Results in death	
b. Is life-threatening	
 
The term 'life-threatening' in the definition of 'serious' refers to an event in which the patient was at risk of death at the time of the event. It does not refer to an event, which hypothetically might have caused death, if it were more severe.
 

c. Requires inpatient hospitalization or prolongation of existing hospitalization	
 
In general, hospitalization signifies that the patient has been detained (usually involving at least an overnight stay) at the hospital or emergency ward for observation and/or treatment that would not have been appropriate in the physician's office or outpatient setting. Complications that occur during hospitalization are AEs. If a complication prolongs hospitalization or fulfills any other serious criteria, the event is serious. When in doubt as to whether "hospitalization" occurred or was necessary, the AE should be considered serious.
 
Hospitalization for elective treatment of a pre-existing condition that did not worsen from baseline is not considered an AE.
 

d. Results in persistent disability/incapacity	
 
The term disability means a substantial disruption of a person's ability to conduct normal life functions.
 
This definition is not intended to include experiences of relatively minor medical significance such as uncomplicated headache, nausea, vomiting, diarrhea, influenza, and accidental trauma (eg, sprained ankle) which may interfere with or prevent everyday life functions but do not constitute a substantial disruption.
 

e. Is a congenital anomaly/birth defect	
f. Important medical event	
 
Medical or scientific judgment should be exercised in deciding whether SAE reporting is appropriate in other situations such as important medical events that may not be immediately life-threatening or result in death or hospitalization but may jeopardize the patient or may require medical or surgical intervention to prevent one of the other outcomes listed in the above definition. These events should usually be considered serious.
 
 
Examples of such events include invasive or malignant cancers, intensive treatment in an emergency room or at home for allergic bronchospasm, blood dyscrasias, or convulsions that do not result in hospitalization, or development of drug dependency or drug abuse.

**Recording and AE and/or SAE****AE and SAE Recording**

- When an AE/SAE occurs, it is the responsibility of the investigator to review all documentation (eg, hospital progress notes, laboratory reports, and diagnostics reports) related to the event.
- The investigator will then record all relevant AE/SAE information in the eCRF.
- It is **not** acceptable for the investigator to send photocopies of the patient's medical records in lieu of completion of the AE/SAE CRF page.
- There may be instances when copies of medical records for certain cases are requested. In this case, all patient identifiers, with the exception of the patient number, will be redacted on the copies of the medical records before submission.
- The investigator will attempt to establish a diagnosis of the event based on signs, symptoms, and/or other clinical information. Whenever possible, the diagnosis (not the individual signs/symptoms) will be documented as the AE/SAE.

**Assessment of Intensity**

Intensity of all AEs including clinically significant treatment-emergent laboratory abnormalities, injection site reactions and potential systemic reactions will be graded according to the National Cancer Institute Common Terminology Criteria for Adverse Events (CTCAE), Version 5.0. The CTCAE grade refers to the severity of the AE and ranges from Grade 1 (mild AE), Grade 2 (moderate AE), Grade 3 (severe AE) and Grade 4 (life-threatening or disabling AE) to Grade 5 (death related to AE).

Adverse events not listed by the CTCAE will be graded as follows:

- Mild: An event that is easily tolerated by the patient, causing minimal discomfort and not interfering with everyday activities.
- Moderate: An event that causes sufficiently discomfort and interferes with normal everyday activities.
- Severe: An event that prevents normal everyday activities. An AE that is assessed as severe should not be confused with a SAE. Severe is a category utilized for rating the intensity of an event; and both AEs and SAEs can be assessed as severe.
- An event is defined as 'serious' when it meets at least 1 of the predefined outcomes as described in the definition of an SAE, NOT when it is rated as severe.

**Assessment of Causality**

- The investigator is obligated to assess the relationship between trial treatment and each occurrence of each AE/SAE.
- A "reasonable possibility" of a relationship conveys that there are facts, evidence, and/or arguments to suggest a causal relationship, rather than a relationship cannot be ruled out.
- The investigator will use clinical judgment to determine the relationship.
- Alternative causes, such as underlying disease(s), concomitant therapy, and other risk factors, as well as the temporal relationship of the event to trial treatment administration will be considered and investigated.
- The investigator will also consult the Investigator's Brochure (IB) and/or Product Information, for marketed products, in his/her assessment.

### Assessment of Causality

- For each AE/SAE, the investigator **must** document in the medical notes that he/she has reviewed the AE/SAE and has provided an assessment of causality.
- There may be situations in which an SAE has occurred, and the investigator has minimal information to include in the initial report. However, **it is very important that the investigator always make an assessment of causality for every event before the initial transmission of the SAE data.**
- The investigator may change his/her opinion of causality in light of follow-up information and send a SAE follow-up report with the updated causality assessment.
- The causality assessment is one of the criteria used when determining regulatory reporting requirements.

A medically qualified Investigator must assess the relationship of any AE (including SAEs) to the use of the trial treatment, as related or not related, based on clinical judgment and using all available information, and may include consideration of the following factors:

- Possible alternative causes of the AE, including the disease under treatment, pre-existing conditions, concomitant use of other drugs, and presence of environmental or genetic factors.
- The temporal association between trial treatment exposure and onset of the AE.
- Whether the manifestations of the AE are consistent with known actions or toxicity of the trial treatment.
- The AE resolved or improved with decreasing the dose or stopping use of the trial treatment (dechallenge). Judgment should be used if multiple products are discontinued at the same time.

The causal relationship between the trial treatment and the AE will be assessed using one of the following categories:

- **Not Related:** Factors consistent with an assessment of Not Related include:
  - Temporal relationship is lacking (eg, the event did not occur within a reasonable time frame following administration of the trial treatment); or
  - Other causative factors more likely explain the event (eg, a pre-existing condition, other concomitant treatments).
- **Related:** Factors consistent with an assessment of Related include:
  - There is a “reasonable possibility” of a relationship; ie, there are facts, evidence, and/or arguments to suggest a causal relationship (not just that “a relationship cannot be ruled out”);
  - There is a positive temporal relationship (eg, the event occurred within a reasonable time frame following administration of trial treatment);
  - The AE is more likely explained by the investigational product than by another cause (ie, the AE shows a pattern consistent with previous knowledge of the investigational product or the class of the trial treatment).

**Follow-up of AEs and SAEs**

- The investigator is obligated to perform or arrange for the conduct of supplemental measurements and/or evaluations as medically indicated or as requested to elucidate the nature and/or causality of the AE or SAE as fully as possible. This may include additional laboratory tests or investigations, histopathological examinations, or consultation with other health care professionals.
- If a patient dies during participation in the trial or during a recognized follow-up period, the investigator will provide a copy of any post-mortem findings including histopathology.
- New or updated information will be recorded in the originally completed CRF.
- The investigator will submit any updated SAE data to the Sponsor within 24 hours of receipt of the information.

**Reporting of SAEs****SAE Reporting via an Electronic Data Collection Tool**

- The primary mechanism for reporting an SAE will be the electronic data collection tool.
- If the electronic system is unavailable for more than 24 hours, then the site will use the paper SAE data collection tool (see next section).
- The site will enter the SAE data into the electronic system as soon as it becomes available.
- After the trial is completed at a given site, the electronic data collection tool will be taken off-line to prevent the entry of new data or changes to existing data.
- If a site receives a report of a new SAE from a trial patient or receives updated data on a previously reported SAE after the electronic data collection tool has been taken off-line, then the site can report this information on a paper SAE form (see next section) or by telephone.

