### 6.10.1. Time Period and Frequency for Collecting AE and SAE Information

All AEs, including SAEs, will be collected from the provision of informed consent/assent until the SFV at the time points designated in the SoAs ([Table 1](#), [CCI](#)). AEs reported after dosing on Day 1 will be considered TEAEs.

Medical occurrences that begin before the start of trial treatment will be recorded on the Medical History/Current Medical Conditions section of the eCRF (not the AE section).

All SAEs will be recorded and reported to the Sponsor or designee within 24 hours, as indicated in [Appendix 5](#). The Investigator will submit any updated SAE data to the Sponsor within 24 hours of it being available.

Investigators are not obligated to actively seek AE or SAE in former trial patients. However, if the Investigator learns of any SAE, including a death, at any time after a patient has been discharged from the trial, and he/she considers the event to be reasonably related to the trial treatment or trial participation, the Investigator must promptly notify the Sponsor.

The method of recording, evaluating, and assessing causality of AE and SAE and the procedures for completing and transmitting SAE reports are provided in [Appendix 5](#).

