**SAE Reporting to via Paper CRF**

- Facsimile transmission of the SAE paper CRF is the preferred method to transmit this information
- In rare circumstances and in the absence of facsimile equipment, notification by telephone is acceptable with a copy of the SAE data collection tool sent by overnight mail or courier service.
- Initial notification via telephone does not replace the need for the investigator to complete and sign the SAE CRF pages within the designated reporting time frames.
- Contacts for SAE reporting will be provided to sites.

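### Appendix 5 directs sites to the paper SAE form only after an electronic outage of more than 24 hours, so a site that follows this trigger can miss the protocol's 24-hour SAE limit

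*Protocol*

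**What the plan says.** Section 6.10.1 of the protocol sets the limit: "All SAEs will be recorded and reported to the Sponsor or designee within 24 hours". It adds that this is to be done as set out in Appendix 5, but does not say from what moment the 24 hours run for a first report. For follow-up data it does give a start: "The Investigator will submit any updated SAE data to the Sponsor within 24 hours of it being available". Appendix 5, under the heading on follow-up of AEs and SAEs, has a slightly different one: "The investigator will submit any updated SAE data to the Sponsor within 24 hours of receipt of the information".

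Appendix 5 then describes the routes.

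- Electronic: "The primary mechanism for reporting an SAE will be the electronic data collection tool".
- Paper during the trial: "If the electronic system is unavailable for more than 24 hours, then the site will use the paper SAE data collection tool".
- Paper or telephone after the site has finished: this allowance follows the statement "After the trial is completed at a given site, the electronic data collection tool will be taken off-line", so it does not concern an outage while the trial is running.
- Fax is the preferred way to send the paper form. Telephone is a narrower option: "In rare circumstances and in the absence of facsimile equipment, notification by telephone is acceptable". A call alone is not enough, because it "does not replace the need for the investigator to complete and sign the SAE CRF pages within the designated reporting time frames".

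**The concern.** Section 6.10.1 sends the site to Appendix 5 for the procedure that delivers the 24-hour report. In Appendix 5 the trigger for the backup is an outage longer than 24 hours, so waiting for it can use up the whole allowance. An outage of 24 hours or less has no stated backup, although it too can run past the deadline of an SAE that was already known and waiting to be entered.

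The stake is how soon the Sponsor learns of a serious event. Section 6.10.6 calls prompt notification essential to regulatory obligations and patient safety. Under Section 5.5.2.3 the Sponsor lifts the blind for the individual patient after an unexpected treatment-related SAE, which it cannot do before it hears of the event. The site is also left in an awkward position: waiting for the Appendix 5 trigger may breach Section 6.10.1, while sending paper sooner means acting without a written direction to do so.

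**Working it through.** The plan states no figure to reproduce. The check sets the two clocks against each other.

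**Inputs**

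- Reporting limit: 24 hours (Section 6.10.1).
- Paper trigger: electronic system unavailable for more than 24 hours (Appendix 5).
- Assumption: the limit for a first report runs from site awareness.
- *a*: hours from the start of the outage to awareness. It is negative if the site knew before the outage and had not yet entered the SAE. Only *a* > −24 is of interest, since otherwise the deadline had passed before the system failed.
- *L*: length of the outage in hours. The documents give no outage frequency or duration, so *a* and *L* are illustrative.

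**Formulas**, in hours from the start of the outage

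- Deadline = 24 + *a*.
- Paper trigger met after hour 24, and only if *L* > 24.
- Time left when the trigger is met: at most (24 + *a*) − 24 = *a*.
- Trigger measured from awareness: more than 24 − *a* hours.

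**Cases**

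| Awareness | Outage | Deadline (outage hour) | First stated route | Result |
|---|---|---|---|---|
| 12 h before (*a* = −12) | *L* = 20 | 24 − 12 = 12 | System returns at hour 20; paper never triggered | 20 − 12 = 8 h late |
| 6 h before (*a* = −6) | *L* > 24 | 24 − 6 = 18 | Paper, after hour 24 | More than 24 − 18 = 6 h late |
| At the start (*a* = 0) | *L* > 24 | 24 | Paper, after hour 24 | Missed |
| 6 h into it (*a* = +6) | *L* > 24 | 24 + 6 = 30 | Paper, after hour 24 | At most 30 − 24 = 6 h left; can be met |
| After hour 24 (*a* > 24) | Still down | 24 + *a* | Paper, already triggered | Full 24 h available |

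**General result**

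- For a site that waits for the trigger, a miss is forced when *a* ≤ 0 and *L* > 24 + *a*.
- If *a* ≤ 0 and *L* < 24 + *a*, the system returns before the deadline and the report can be entered on time.
- If 0 < *a* < 24 and *L* ≤ 24, the system is back by hour 24, before the deadline of 24 + *a*.
- If 0 < *a* < 24 and *L* > 24, the usable window shrinks to at most *a* hours.

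**Other routes.** Neither remaining allowance closes the gap. Telephone is limited to rare circumstances without fax equipment and leaves the signed form due within the same time frame. The off-line allowance begins only when the trial is complete at the site.

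The same comparison applies to follow-up SAE data sent through the same tool. There the documents do state a start for the clock: when the data are available in Section 6.10.1, on receipt in Appendix 5.

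**The case against.** The strongest reply is that the two passages do not conflict. Appendix 5 says when paper must be used; it does not say that paper may not be used sooner. The electronic tool is called the primary mechanism, not the sole one. The duty in Section 6.10.1 has no exception for outages, so a site can satisfy both passages by sending the form early. Section 6 also asks that immediate safety concerns be discussed with the Sponsor at once, Appendix 5 promises reporting contacts, and the telephone option does not depend on how long an outage has lasted.

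Much of this stands. A reader might infer that Appendix 5 prohibits paper during the first 24 hours, and the text does not support that. Nor does it make a late report inevitable, or show that the Sponsor could not hear of the event informally. What remains is that Section 6.10.1 names Appendix 5 as the procedure, and Appendix 5 gives no direction for an outage of 24 hours or less. The Section 6 sentence is about whether a patient should stay on treatment and is not a formal SAE route.

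Three further inferences also go too far.

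- **A typical delay of about 48 hours.** As *a* approaches −24, the trigger comes 24 + 24 = 48 hours after awareness. That requires a site that first tries to enter the SAE as its time runs out, a failure at that moment, and an outage of more than a day. By then the site has used up its own allowance.
- **Harm to DSMB oversight.** Section 6.9 has the board meeting about every 3 months on cumulative data. A delay of a day or so gives little ground for that claim.
- **A breached regulatory deadline.** Section 6.10.6 leaves SUSAR reporting to local requirements and states no time limit, so the documents cannot show one.

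**Conclusion.** The point holds in a limited form. The stated trigger for paper can defeat the protocol's own 24-hour limit, and no formal route is given for a shorter outage during the trial. For a site that follows the trigger, the miss is certain only if the SAE was known at or before the start of the outage, had not been entered, and the outage lasts beyond the deadline. In the worked cases the report is 8 hours late (a 20-hour outage) or more than 6 hours late (an outage over 24 hours). When awareness comes within the first 24 hours of the outage, the window is shortened but the limit can still be met.

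This rests on two things: that the clock for a first report starts at site awareness, and that the site reads Appendix 5 as telling it when to turn to paper. How often such outages occur cannot be judged from the documents. This is an operational weakness in safety reporting that should be corrected. It has no bearing on power, type I error or the efficacy analyses.

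**What to change.** Change the trigger in Appendix 5. Whenever the electronic system is unavailable and waiting for it would put the 24-hour limit at risk, the site completes the paper SAE form, sends it by the routes Appendix 5 already describes, and enters the data electronically once the system is back. In Section 6.10.1, state when the 24 hours begin for a first report, and use one start point for follow-up data in both places.

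The paper form and fax route exist already, and Appendix 5 says contacts will be provided, so nothing new has to be built. The costs are some duplicate paper and electronic entry and a short text change. Appendix 6 requires IRB/IEC approval of amendments, so the wording can go into the next planned amendment, with a memo to sites in the meantime.

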**SAE Reporting to via Paper CRF**

- Facsimile transmission of the SAE paper CRF is the preferred method to transmit this information
- In rare circumstances and in the absence of facsimile equipment, notification by telephone is acceptable with a copy of the SAE data collection tool sent by overnight mail or courier service.
- Initial notification via telephone does not replace the need for the investigator to complete and sign the SAE CRF pages within the designated reporting time frames.
- Contacts for SAE reporting will be provided to sites.

